#### 8.7 Follow-up of Serious Adverse Events/Reactions

The patient must be followed-up until clinical recovery is complete and laboratory results have returned to normal, or until disease has stabilised. Follow-up SAE reports should be submitted to the sponsor, as specified in section 8.4. The first follow-up report is expected 10 days from the onset of the event unless it is a SUSAR then the follow up should be sent within 5 days with subsequent submissions as and when there is a significant change or update to the SAE,

#### 8.8 Annual Reporting of Serious Adverse Events/Reactions

An annual Development Safety Update Report (DSUR) will be submitted to the MHRA and the main REC by the sponsor on the anniversary of the date when the Clinical Trials Authorisation (CTA) was obtained. This will include all SARs and SUSARs.

#### 9 END OF TREATMENT (EOT)

End of treatment for a patient is defined as no later than 6 weeks after the first day of the last treatment cycle. The reason for treatment discontinuation will be documented on the appropriate CRF.

#### 9.1 Permanent treatment discontinuation from the IMP

Permanent treatment discontinuation is any treatment discontinuation associated with the definitive decision from the investigator or the patient not to re-expose the patient to the IMP at any time.

If a patient shows one of the following reasons, the study treatment must be discontinued:

- Progression of basal cell carcinoma as per clinical response criteria/RECIST 1.1/composite response criteria (unless continuation of cemiplimab is deemed to be of clinical benefit e.g. it is within the first 12 weeks of treatment (scan 1) and thought to be pseudo-progression, in which case it should be discussed with the CI or nominated representative).
- Unacceptable toxicity or adverse event requiring discontinuation of treatment
- Patient requests to stop treatment including if they change their mind about wanting curative surgery e.g. if the surgery is curative but potentially disfiguring
- Patient shows non-compliance (including persistent patient attendance failure).

The patients may withdraw from treatment with IMP at any time and irrespective of the reason, or this may be the investigator's decision. The reason for treatment discontinuation will be documented as far as possible on the appropriate eCRF.

Further medical or surgical treatment following trial immunotherapy is at the discretion of the treating clinician in consultation with the patient.

#### 9.1.1 Handling of patients after permanent treatment discontinuation

In the case of permanent treatment discontinuation patients should be followed up according to the study procedures as specified in this protocol. The patient will be assessed according to the procedures set out for the end of treatment visit and then enter the follow up period.

#### 9.2 Procedure for withdrawal of patients from study

The patients may withdraw from the study, before study completion if they choose to do so, at any time and irrespective of the reason, or at the investigator's decision. All study withdrawals should be documented by the investigator in the source data but it should be very clear what the patient is withdrawing from – trial treatment, follow up visits, survival status data collection. A patient can withdraw from trial treatment but continue to be followed up with data collected according to the protocol, likewise

if a patient does not want any further follow up procedures but is happy to have progression and survival status collected then this should be recorded.

#### 9.2.1 Consequence

Patients who have been withdrawn from the study cannot be re-included in the study. Their inclusion and treatment number must not be reused. In specific situations to be discussed between the investigator and the sponsor, patients who have not yet been registered can be re-included in the study.

# 10 END OF STUDY (EOS)

Recruitment is planned for 24 months. Patients will be treated for up to 24 months and then followed up every 3 months for a further 12 months. Survival follow up will then be conducted at 18 and 24 months post end of treatment. The end of study is defined as last patient last visit (LPLV) which will be the last survival follow up visit (at 24 months after end of treatment) completed by a patient on the trial.

#### 10.1 Premature Termination of Study

The study may be terminated prematurely for safety reasons, slow accrual, or upcoming new data impairing the relevance of the study objective, by the University Hospitals Bristol and Weston NHS Trust (UHBW) as the sponsor, or the data monitoring committee. The Independent Data Monitoring Committee will provide advice. The sponsor is allowed to close the trial for any reason at any time. A decision to prematurely terminate the study is binding to all investigators of all study sites. Responsible ethics committees and regulatory authorities will be informed about the reason(s) and time of termination according to the applicable laws and regulations.

#### 10.2 Premature Termination of Study at a Particular Study Site

The sponsor (UHBW) reserves the right to discontinue the study at a particular study site at any time. The reasons will be discussed with the investigator.

The sponsor (UHBW) may terminate this study in one particular study site for one of the following reasons:

- Non-compliance with GCP and/or regulatory requirements.
- Insufficient number of recruited patients.
- Failure to comply with trial protocol and guidelines
- Inadequate co-operation with UHBW or its representatives.
- The Investigator requests to close his/her study site.

If the study is prematurely terminated in a study site, the responsible investigators have to inform their patients and take care of appropriate follow-up and further treatment of the patients.

#### 11 STATISTICAL CONSIDERATIONS

The statistical analysis of the present study is performed in accordance with the principles stated in the Consensus guideline E9 (Statistical Principles for Clinical Trials) of the International Conference on Harmonisation (ICH).

# 11.1 Sample size calculations

The hedgehog pathway inhibitors (HHIs) have shown an ORR of about 45% in the first line setting. In the ERIVANCE study, the ORR with vismodegib was 42.9% at 9 months follow-up which increased to 47.6% at 21 months follow-up (9). In the BOLT study of sonidegib, the ORR was 47.0% at primary 6 month follow-up, increasing to 56.1% (95% CI: 43.3–68.3) at 18 month follow-up (10). In the second line setting, cemiplimab showed an ORR of 31%, in a recently reported phase 2 study in the 2nd line setting (18), after a median follow-up of 15 months.

Assuming an ORR of cemiplimab to be around 45% at 6-months in the first line setting, this study is powered as a single arm Simon II Stage design. This will be used to differentiate between a poor treatment (success rate of 25%) and a good treatment (success rate 45%) using a nominal significance level alpha = 5% and a power of 80%.

Once 18 patients are recruited, an interim analysis will be performed with the decision rule of progression to Stage II if 6 or more of the 18 patients achieve a response. If ≤5 patients have responded (poor response) or if 15 out of the 18 patients have responded (exceptional response) the trial will be stopped.

Stage II will be the recruitment of a further 19 patients. To account for a potential loss of non-evaluable patients (assuming a 10% drop out rate) the sample size will be inflated to N = 41.

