# 2.3 Secondary endpoints

- To evaluate safety and tolerability including the frequency, severity and relatedness of AEs to the study treatment. AEs will be assessed according to CTCAE v5.0.
- To assess ORR at 12 months and 24 months.
- To assess disease control rate (DCR) at 6, 12 and 24 months. DCR is ORR plus stable disease (SD).
- To assess progression-free survival (PFS) defined as the time from registration to the first of one of the following: development of clinical/radiological disease progression (composite criteria/ RECIST 1.1) or death from any cause.
- To assess overall survival (OS) defined as time from registration to the date of death from any cause.
- To assess patient health status and quality of life (QoL) using the patient reported outcome measures EQ-5D-5L, EORTC QLQ-C30, Skindex-16, FNAE and the Hornheide questionnaire.
- To estimate the time to response (TTR: defined as the time from the start of treatment to the first objective tumour response (tumour shrinkage of ≥30%)) and duration of response (DOR: the time from response to progression/death) to cemiplimab.

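### The interim rule in section 11.1 contradicts itself at 15 of 18 responders, literally continues at 16 to 18, and does not say what stopping covers

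*Protocol*

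**What the plan says.** Protocol section 11.1 (Sample size calculations) states that "this study is powered as a single arm Simon II Stage design", to tell a response rate of 25% from one of 45% with alpha 5% and power 80%. An interim analysis follows the recruitment of 18 patients, and two sentences then fix the decision:

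- Continue: "progression to Stage II if 6 or more of the 18 patients achieve a response".
- Stop: at 5 or fewer responders, written with an inequality sign; the same sentence adds that "if 15 out of the 18 patients have responded (exceptional response) the trial will be stopped".

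The second stage is described as recruiting 19 more patients, which gives 37 evaluable and 41 after allowance for dropout. Section 11.1 states no final cut-off.

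The later endpoints that depend on continued follow-up are in section 2.3: "To assess ORR at 12 months and 24 months", together with disease control rate, PFS, OS and duration of response.

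**The concern.** Three things in the rule do not fit together.

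1. **Overlap at 15.** The continue rule has no upper limit, so 15 responders fall under both instructions.
2. **Gap at 16 to 18.** The lower stopping limit carries an inequality and the upper one, in the same sentence, does not. Taken literally, 16, 17 or 18 responders meet only the continue rule.
3. **Undefined action.** One phrase covers both futility and exceptional response. It does not say whether it ends recruitment alone or also the follow-up of patients already in the trial.

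A pre-specified stopping rule should not need interpretation once the counts are known, because an interpretation chosen then can look data-driven. What is at stake is a clear interim decision and certainty that the first 18 patients still supply the 12- and 24-month data.

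**Working it through.** **Inputs from section 11.1.** Null rate p0 = 0.25, target rate p1 = 0.45, n1 = 18, stop at 5 or fewer, n = 37. Alpha is taken as one-sided, as is usual for a Simon design; the protocol does not state sidedness.

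**Step 1: reproduce the stated design.** With X1 ~ Bin(18, p) and X2 ~ Bin(19, p), the probability of declaring success with final cut-off c is

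sum over x = 6 to 18 of P(X1 = x) × P(X2 ≥ c − x).

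| Final cut-off c of 37 | Alpha (p = 0.25) | Power (p = 0.45) |
|---|---|---|
| 13 | 0.0876 | 0.852 |
| 14 | 0.0496 | 0.806 |
| 15 | 0.0249 | 0.732 |

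Only c = 14 meets both 5% and 80%. The design reproduces, with a derived cut-off of 14 of 37. The probability of stopping at 5 or fewer is 0.717 at 25% and 0.108 at 45%.

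**Step 2: apply the two sentences to every possible count.**

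| Responders of 18 | Continue rule | Stop rule | Literal result |
|---|---|---|---|
| 0–5 | no | yes | stop |
| 6–14 | yes | no | continue |
| 15 | yes | yes | contradiction |
| 16–18 | yes | no | continue |

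**Step 3: how often the affected counts occur.** P(X1 = k) = C(18, k) p^k (1 − p)^(18 − k). For example, at p = 0.45, P(15) = 816 × 0.45^15 × 0.55^3 = 0.00085.

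| True response rate | Source | P(15) | P(16–18) | P(≥15) |
|---|---|---|---|---|
| 25% | null rate | 3.2 × 10⁻⁷ | 2.1 × 10⁻⁸ | 3.4 × 10⁻⁷ |
| 45% | planned rate | 0.00085 | 0.00014 | 0.0010 |
| 56.1% | highest rate quoted in 11.1 | 0.0118 | 0.0033 | 0.015 |
| 80% | assumed, illustration only | 0.230 | 0.271 | 0.501 |
| 85% | assumed, illustration only | 0.241 | 0.480 | 0.720 |

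The last two rows appear nowhere in the protocol. They show only that in the situation the upper rule was written for, the unclear counts would not be rare.

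**Step 4: effect of the repair on the error rates.** If 15 or more of 18 counts as success without Stage II, alpha stays at 0.0496 and power at 0.806. The reason is that 15 already exceeds 14, so every path through 15 to 18 ends in success whether or not Stage II is run.

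**Step 5: what stopping means, from the other sections.**

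- Section 11.1 frames the interim decision as moving to Stage II, and Stage II as more recruitment. That favours the reading that stopping means not opening Stage II.
- Section 9.1.1 keeps patients in follow-up after they permanently stop treatment, but it concerns individual patients, not a trial-level stop.
- Section 10 places the end of study at the last survival visit, 24 months after end of treatment, and does not mention an interim stop.
- Section 10.1 does not list efficacy among its named grounds for premature termination, though the sponsor may close the trial for any reason. It is silent on follow-up of registered patients.

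No section settles the question. The balance points towards continued follow-up.

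**The case against.** The strongest reply is that the intent is plain. The label of exceptional response marks 15 as a threshold, no committee would stop at 15 and continue at 18, and the second sentence can be read as listing exceptions to the general continue rule. The probability at plausible response rates is tiny and the error rates are untouched. All of this stands, and it is why the point is minor. It does not make the text consistent: the authors wrote an inequality for the lower limit and none for the upper.

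Two stronger readings are tempting and are not supported.

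- A reader might infer that the rule ends the whole trial and so loses 12- and 24-month response, PFS, OS and duration of response when the drug works best. No section says so, and sections 9.1.1, 10 and 11.1 lean the other way. That inference also clashes with the literal gap: if 15 means exactly 15, then 16 to 18 continue and nothing is lost there; if it means 15 or more, the gap disappears. The supportable statement is that the phrase is ambiguous.
- A reader might argue that there should be no efficacy stop at all, since 14 of 18 already secures the derived cut-off and 18 patients give less precision and safety information than 37. That is a preference between designs. Stopping at 15 or more is statistically safe, and choosing to do so is not an error.

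**Conclusion.** The inconsistency is real and can be read directly from section 11.1: 15 of 18 is told both to continue and to stop, 16 to 18 literally continue, and the scope of stopping is undefined. Its practical size is small. The upper region is reached with probability 0.0010 at the planned 45% and 0.015 at 56.1%. The literal gap at 16 to 18 has probability 0.00014 and 0.0033 at those rates. Alpha, power and sample size are unaffected.

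These figures rest on exact binomial counts, a one-sided test and a final cut-off of 14 of 37, which the protocol does not state. The documents do not establish any loss of later endpoints. This is a clarification of a decision rule, worth making because it is nearly free and because the rule is operative at the interim.

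**What to change.** Replace the two sentences in section 11.1 with a rule that covers each count once:

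- 6 to 14 of 18 respond: continue to Stage II.
- 5 or fewer respond: do not open Stage II.
- 15 or more respond: do not open Stage II, and conclude efficacy.

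Add that stopping under this rule closes recruitment only, and that registered patients keep their planned assessments and follow-up, so that 12- and 24-month response, PFS, OS and duration of response are still collected. A cross-reference in section 10.1 would remove the remaining doubt. How trial treatment of registered patients is handled after such a stop is a clinical matter for the investigators and sponsor to state.

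The cost is a sentence or two of protocol text, with no change to alpha, power or sample size. It should be done before the 18-patient interim counts are known.

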#### 4.2 Number of patients

41 patients will be recruited across multiple sites, aiming to recruit 37 evaluable patients.

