#### 11.7 Frequency of analyses

The Trial Management Group and Trial Steering Committee will meet at least annually to examine patient recruitment, safety and efficacy. The Independent Data Monitoring Committee will meet 6 months after the FPFV, to assess safety data in particular and then at least annually thereafter. An interim report will be prepared after 18 patients have been recruited into the study (see section 11.1).

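### The stage 1 rule is tied to 18 recruited patients while the 10% non-evaluable allowance is added only to the total; unless replacement is completed before the interim, power could fall from 80.6% to about 74%

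*Protocol*

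**What the plan says.** Section 11.1 sets a Simon two-stage design to separate response rates of 25% and 45% with a nominal alpha of 5% and 80% power. Stage 1 is 18 patients and stage 2 a further 19.

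- Interim trigger (11.1): "Once 18 patients are recruited, an interim analysis will be performed". Section 11.7 repeats it: "An interim report will be prepared after 18 patients have been recruited into the study".
- Stage 1 rule (11.1): "decision rule of progression to Stage II if 6 or more of the 18 patients achieve a response". With five or fewer responses the trial stops. It also stops for an exceptional result at 15 of 18.
- Loss allowance (11.1): "To account for a potential loss of non-evaluable patients (assuming a 10% drop out rate) the sample size will be inflated to N = 41".
- Evaluable target (4.2): "41 patients will be recruited across multiple sites, aiming to recruit 37 evaluable patients".
- Replacement (11.6): non-evaluable patients are to be replaced after central review of all patients by the Trial Management Group. The sentence is framed for the principal analysis and does not mention the interim.
- Analysis set (11.2): intention to treat.

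**The concern.** Since 18 + 19 = 37 and section 4.2 calls 37 an evaluable number, the 18 in the design should be evaluable patients too. Sections 11.1 and 11.7 use it as a number recruited. The allowance lifts the total from 37 to 41, but the four extra patients are assigned to neither stage, and the stage 1 count and its boundary of six responses are unchanged.

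A patient who cannot be evaluated cannot supply a response. If such patients stay among the 18, six responses must come from fewer patients than the boundary was built for, so the futility rule is stricter than designed. A futility stop ends the trial, and patients planned for later cannot reverse it. This is separate from when the 6-month responses become available: with full follow-up of all 18, a 10% loss still leaves about two without an evaluable response.

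**Working it through.** **Inputs.** From 11.1: p0 = 0.25, p1 = 0.45, n1 = 18, continue if at least 6 respond, n2 = 19, loss 10%, N = 41. From 4.2: 37 evaluable. Assumed: alpha is one-sided (sidedness is not stated); the final cut-off is at least 14 of 37 (not stated); loss is independent of response.

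**1. Reproduce the design.** The probability of a positive trial is the sum over x ≥ 6 of P(Bin(18, p) = x) × P(Bin(19, p) ≥ 14 − x).

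- At p = 0.25: 0.0496. A final cut-off of 13 would give 0.0876, so 14 is the lowest cut-off that keeps alpha within 5%.
- At p = 0.45: 0.806.
- Early stop at p = 0.45: P(Bin(18, 0.45) ≤ 5) = 0.108.
- The upper stop at 15 of 18 changes nothing material.
- Inflation: 37 × 1.1 = 40.7, rounded up to 41. Dividing instead gives 37/0.9 = 41.1. The difference is immaterial here.

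The stated design therefore holds when 18 and 37 are evaluable counts.

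**2. Leave 10% non-evaluable among the 18, unreplaced.**

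- Each recruited patient yields a response with probability 0.45 × 0.9 = 0.405.
- Early stop: P(Bin(18, 0.405) ≤ 5) = 0.197, against 0.108. The ratio is 1.83.
- The chance that at least one of the 18 is non-evaluable is 1 − 0.9^18 = 0.85.

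Power was computed in three ways, all with a final cut-off of 14:

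- (a) 41 recruited, non-evaluable patients counted as non-responders: 0.735.
- (b) stage 1 evaluable count distributed as Bin(18, 0.9), total made up to exactly 37 evaluable: 0.739.
- (c) exactly 16 evaluable at stage 1, total 37 evaluable: 0.741.

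**3. Vary the loss rate.**

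| Loss | Stop at 45% | Power (a), 41 recruited | Power (b), 37 evaluable |
|---|---|---|---|
| 0% (as designed, 37 patients) | 10.8% | 80.6% | 80.6% |
| 5% | 14.8% | 80.8% | 77.7% |
| 10% | 19.7% | 73.5% | 73.9% |
| 15% | 25.5% | 64.6% | 69.2% |

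The 80.8% at 5% loss arises because 41 recruited then yield about 39 evaluable patients (41 × 0.95) against an unchanged cut-off of 14. The type I error in that case is 6.5%.

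**4. Replace non-evaluable stage 1 patients before the decision.** Stage 1 again has 18 evaluable patients. The stop rate is 10.8% and, with 37 evaluable in total, power is 80.6%.

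**5. Test the fix.** Take 18 evaluable patients at stage 1 (18/0.9 = 20 registered). The remaining 41 − 20 = 21 registered patients are each evaluable with probability 0.9, and the final cut-off is 14. Power is 0.799 and alpha 0.0495.

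**The case against.** The strongest reply is that the word recruited is used loosely. Section 11.1 also speaks of recruiting the further 19, and 18 + 19 is the number that 4.2 calls evaluable. On that reading 18 is already an evaluable count, the inflation covers both stages, and nothing is lost. Section 11.6 supports this, because the Trial Management Group reviews all patients, which includes the first 18, and no text suspends replacement at the interim. This part stands: under that reading power is 80.6%, so a reader who inferred that the trial's power simply is 73–74%, or that an active drug will be stopped about twice as often, would go further than the documents allow.

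It does not remove the point. Both places that set the trigger say recruited and neither mentions evaluability, while the replacement sentence is confined to the principal analysis. A team following 11.1 and 11.7 literally would apply a boundary built for 18 evaluable patients to about 16.

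Three further replies:

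- **The 10% is an allowance, and 11.6 defines non-evaluable narrowly.** True, and at 5% loss the effect is small. But 10% is the plan's own figure.
- **Intention to treat settles it.** It does not. If non-evaluable patients count as non-responders, that is calculation (a), with power 73.5% at 10% loss.
- **The interim analysis set can be left to the SAP or a committee charter.** A missing detail could be. Here the protocol itself states a stopping rule and its denominator, and these do not match its own evaluable target.

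**Conclusion.** The point holds in conditional form. No stated figure is miscalculated: 18/37 with a go rule of six reproduces 80% power, and 41 is a fair inflation of 37. The fault is that 11.1 and 11.7 (18 recruited), 4.2 (37 evaluable) and 11.6 (replacement) are not reconciled for the stage 1 decision.

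Read literally at the plan's own 10% loss, a drug with a true 45% response rate is stopped at stage 1 about one time in five instead of one in nine, and power is about six to seven points below the stated 80%. With replacement completed first, there is no loss. The documents do not settle which applies.

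The stop rates do not depend on the final cut-off. The power figures do, and they rest on the unstated cut-off of 14 of 37. Both sets of figures assume that loss is unrelated to response. The point deserves correction because the rule decides whether the trial continues and the repair is cheap.

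**What to change.** - In 11.1 and 11.7, apply the stage 1 rule to the first 18 evaluable patients, which means about 20 registered at 10% loss.
- In 11.6, state that review and replacement of non-evaluable patients also apply at the interim and are completed before the stage 1 decision.
- Keep the total at 41. With 10% loss among the remaining patients, power is about 79.9% and alpha about 4.9%.
- If 18 recruited is what is intended, keep it and restate the power as about 73–74% at 10% loss.

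The cost is a wording change. The interim falls about two patients later, and the total sample size does not change.
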